- National Eye Institute Visual Function exams will be administered to each subject as outlined in previous section with and without the head mounted visual assessment device. During the testing portion of the head mounted visual assessment device, head and eye movements will be video recorded by one of the sponsor/manufacturer's agents for this research project.. This will allow the team to assess what kinds of adjustments the subjects are making to optimize their view. Patients will be given a 20-minute break between testing with and without the head mounted visual assessment device.
- Administration and completion of patient questionnaire on their experience with the use of NEI Visual Function exams
- A second study visit identical to this one may be repeated after a period of self-training at home with the device.

Inclusion Criteria:

1. Patient of any sex, race, or ethnicity who are 18 years of age or older. Spanish speaking patients will be encouraged to participate, Spanish forms will be available to review and execute.
2. Patient willing to review, understand, and sign written Informed Consent. Parents or legal guardians will consent on behalf of minors.
3. Written authorization for use or release of health and research study information.
4. Patient who volunteers is suffering from a posterior segment ophthalmic disorder including Retinal Degeneration and/or Diabetic Retinopathy and visual acuity from 20/60 to 20/400 in the better Seeing Eye.

Exclusion Criteria:

1. Subjects will be excluded if they are less than 18 years of age.
2. Subjects will not be considered for this research study if they will not review and execute the informed consent form.
3. During the screening process, subjects will be excluded from further consideration if they are identified with having a potential ophthalmic diagnosis other than Retinal Degeneration or diabetic macular edema that could be negatively affecting the visual testing.
4. ETDRS Visual Acuity better than 20/60 or worse than 20/400
5. During screening, subjects will be disqualified from further assessment if it is determined that their refractive error is outside of the -5.00D to +5.00D corrective range.

Sources of Research Material:

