test, which will last **about 2 hours**. The tester will be constantly supervising the patient during the exam. Another area where there may be an opportunity for potential risk is in protecting patient privacy throughout the course of the study and following the conclusion of the project. A detailed plan is provided in “Procedures to Maintain Confidentiality”.

Subject Safety and Data Monitoring:

Careful oversight of patient safety and wellbeing will be undertaken by the Principal Investigator and Sub-Investigator on this study. In the event of an adverse event during the visits as required by the study protocol, treatment will be provided by the researcher on this study and the affected patient will be stabilized before exited from the study.

Special Precautions:

Procedures to protect against the potential risk of a breach of confidentiality are described in the following section. Any additional physical or psychological risk to patients as a result of this prospective study is not foreseeable as the collection method utilized is typically used in the clinic for standard of care management. Subjects are informed verbally and in the consent form of the following: contact information and the phone number for investigator in case of an adverse event that occurs after the study is initiated. Moreover, the PI will monitor the study for quality assurance purposes.

Procedures to Maintain Confidentiality:

All subject data will remain confidential and access will be restricted to authorized study personnel only, including the principal investigator, sub-investigator, and the study research study. All study information and data will be secured in a locked area and accessible only to study investigators. Patient identifying information will be removed as the pertinent data is transferred to a data collection sheet so that there

is no link to specific identifiers. All electronic study data will be password protected. Data will be presented in aggregate form to the sponsor without specific identifiers.

The Investigator(s) / Institution(s) will permit trial-related monitoring, audits, IRB review and regulatory inspection(s) by providing direct access to source data / documents. Should the clinical site be contacted for an audit by an IRB or regulatory authority, study sponsor should be contacted and notified in writing within 24 hours.

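### Filming by a sponsor's agent is specified for the device condition but not for the no-device condition, so the paired comparison cannot separate any effect of being filmed from the effect of the device.

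*Combined protocol and SAP*

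**What the plan says.** The protocol's Study Procedures section has the visual function tests given to each subject "as outlined in previous section with and without the head mounted visual assessment device". It continues that, during the device portion, "head and eye movements will be video recorded by one of the sponsor/manufacturer's agents". The stated purpose is descriptive: "This will allow the team to assess what kinds of adjustments the subjects are making to optimize their view". On the gap between conditions it says: "Patients will be given a 20-minute break between testing with and without the head mounted visual assessment device". It mentions no recording of the no-device portion and does not say where the agent is at that time.

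The Concise Summary of Project calls the study non-randomized and describes four tests: reading speed, a timed shape board, a timed shelf search repeated three times, and questions about facial expressions after a short silent video. No masking is described.

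The Potential Risks section says of the person running the tests: "The tester will be constantly supervising the patient during the exam". That is not limited to one condition.

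The Statistical Analysis Plan compares device with no device by paired t-test, in a pilot of 8 to 10 subjects that may be expanded to 20. It makes no provision for a difference in filming.

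Procedures to Maintain Confidentiality restricts study data to study investigators and adds: "Data will be presented in aggregate form to the sponsor without specific identifiers".

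**The concern.** In a within-subject comparison the two conditions should differ in the device and in as little else as possible. As written, they also differ in whether a representative of the manufacturer is filming. Three of the four tests are timed and depend on effort. The fourth depends on answers to questions. Subjects know which condition they are in. Being filmed by the maker of the product could make a subject try harder, or could make the subject self-conscious and slower.

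The device and no-device contrast is the only comparison in the study, and filming coincides with the device in every subject. No analysis of these data could therefore separate the two. Balancing the order of conditions would not help either, because the filming follows the device and not the period. The pilot is exposed in the same way, and its result decides whether the study expands.

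**Working it through.** **What the text fixes and what it leaves open**

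| Feature | Device portion | No-device portion | Source |
|---|---|---|---|
| Filming by sponsor's agent | Specified | None described | Study Procedures |
| Agent in the room | Implied by the filming | Not stated | Study Procedures |
| Tester supervising | Yes | Yes | Potential Risks |
| Analysis | Paired t-test between the two portions | (same) | Statistical Analysis Plan |

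The documented difference is filming by the sponsor's agent. One-sided filming is the natural reading, because the sentence names one of the two portions just introduced. It still rests on silence about the other portion.

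**Why the t-test cannot separate the effects.** Let D be a subject's paired difference, device minus no device. Under this plan the mean of D is (device effect) + (filming effect), and the test examines only that sum. No subject has the device without filming, or filming without the device, so the two terms are not separately estimable.

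**Illustration of size.** The plan has no figure to reproduce here: it gives no alpha, power, effect size or SD of the paired difference. From the plan: n = 20, or 8 to 10 in the pilot, and a paired t-test. Assumed: two-sided alpha 0.05, no device effect, and a filming effect of δ SDs of the paired difference.

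Rejection rate = P(|T| > c), where T is noncentral t with n − 1 degrees of freedom and noncentrality δ√n, and c is the 97.5% point of central t. For n = 20, c = 2.093 on 19 df. For n = 10, c = 2.262 on 9 df. For n = 8, c = 2.365 on 7 df.

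| δ (assumed) | δ√20 | n = 20 | n = 10 | n = 8 |
|---|---|---|---|---|
| 0 | 0 | 5.0% | 5.0% | 5.0% |
| 0.1 | 0.447 | 7.1% | 5.9% | 5.7% |
| 0.2 | 0.894 | 13.6% | 8.8% | 7.8% |
| 0.3 | 1.342 | 24.7% | 13.6% | 11.4% |
| 0.4 | 1.789 | 39.7% | 20.5% | 16.6% |
| 0.5 | 2.236 | 56.5% | 29.3% | 23.2% |

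To put δ on a time scale, suppose the SD of the log-time difference were 0.42 (assumed). A 10% reduction in time from being filmed would then be ln(1/0.9)/0.42 = 0.105/0.42 = 0.25 SD, and the rejection rate at n = 20 would be 18.6%. This conversion does not apply to the facial-expression test, which is not timed.

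**The other direction.** With n = 20 the same test has 80% power for a true paired difference of 0.66 SD. If filming hindered performance by 0.1, 0.3 or 0.5 SD, the net differences would be 0.56, 0.36 and 0.16 SD. The same formula gives power of 66%, 33% and 10%. A real benefit could be hidden as readily as a false one is created.

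**The case against.** The strongest reply is that this is a small matter in an open comparison. The wearer always knows the device is on, so expectation is already present, and the added effect of a camera is speculative. The tester watches throughout, so subjects are observed in both conditions. The filming is for engineering description and is not an efficacy outcome. The illustrative shifts come from no source in the documents.

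Much of this stands, and it rules out several stronger readings:

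- **The sponsor is present in one condition only.** A reader might infer this, but the protocol never says that the agent leaves for the no-device portion.
- **Subjects are observed in one condition only.** The constant supervision described under Potential Risks contradicts this. What differs is the camera and who operates it.
- **The bias favours the device.** Nothing in the documents supports a direction.
- **The filming fails its own purpose without a no-device recording.** The stated aim is to describe adjustments, which needs no reference condition. Comparing head and eye movements between conditions would be an optional extra outcome.
- **The sponsor may see nothing but aggregate data, or the consent form omits the filming.** The confidentiality section says how data are presented to the sponsor, and it also allows direct access to source data for monitoring and audit. The consent pages are not in the documents, so their content cannot be judged.

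The reply does not remove the central point. Expectation about the device cannot be avoided in this design; a filming difference can. That other influences are present is no reason to add one that costs little to remove.

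**Conclusion.** The point holds as a possible bias, not a demonstrated one. The protocol specifies filming by a sponsor's agent for the device portion, describes none for the no-device portion, and leaves the agent's presence in the latter unstated. Any resulting effect would be fully confounded with the device effect in the planned test. Across the assumed range of 0.1 to 0.5 SD, a device with no effect would be declared different in 7.1% to 56.5% of trials at n = 20, and in 5.9% to 29.3% at n = 10. These rates assume two-sided alpha 0.05 and show sensitivity; they do not estimate what will happen. If filming has no effect, nothing is lost.

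The correction is worth making because it is cheap and protects the only comparison. The tension between individual recordings made by the sponsor's agent and the confidentiality section is real, but it is a separate matter and adds no weight to the bias argument.

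**What to change.** 1. In Study Procedures, record both conditions with the same camera, the same people present and the same scripted instructions.
2. State that the sponsor's agent does not instruct subjects, time the tasks or score the answers in either condition.
3. Separately, reconcile Study Procedures with Procedures to Maintain Confidentiality by stating who holds the recordings and who may view them.

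The cost is roughly double the recording time, within a visit of about two hours, and the agent's presence for all the testing. No new test or outcome is needed. The downside is more recordings of subjects' heads and eyes to protect, so item 3 should be settled together with item 1.

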This study will be a prospective, non-randomized study of low-vision individuals diagnosed with either retinal degeneration (RDEG) or diabetic macular edema with ETDRS visual acuity from 20/60 to 20/400 in both eyes from the University of Texas - Southwestern (UTSW) Medical Center at Dallas. Specifically, the primary objective of this testing is to establish the benefits of a wide field-of-view (FOV) monocular head-mounted visual enhancement device display (HMD), aiding the most degraded eye, as compared to best corrected visual acuity with glasses. It should be noted that in this approach, the HMD incorporates a camera, mounted coaxially with the visual axis of the eye with worse vision, and also image-enhancing or correction algorithms. Following review and execution of the informed consent, each subject will undergo an examination of their eyes, including: 1) ETDRS Best-corrected

distance visual acuity; 2) Best-corrected near visual acuity; 3) Tests based on questions 5, 6, 7 and 11 of the National Eye Institute 25-item visual function questionnaire (NEI VFQ-25).

- a. Question 5: Reading speed using a standard paragraph

English Paragraph Reference: 3-Minute Reading Assessments, Rasinski TV and Padak N, 2005. Scholastic Inc., NY

Spanish Paragraph Reference: Reference:
<http://www.cuadernosdigitalesvindel.com/libres/lenguaje.php>

Grade 5: Form A

| | |
|---|----|
| Last week, my family went to the county fair. My father is a volunteer firefighter, so he was working at the fair. My mom and sister and I went to meet him. I am very glad we did; it was a great night. When we arrived, the fair was very crowded and finding my dad was like finding a needle in a haystack. We finally found him because we heard the fire truck siren blaring and knew he would be there. Showing off the fire truck is my dad's favorite pastime; that truck is his pride and joy. | 11 |
| | 23 |
| | 37 |
| | 50 |
| | 62 |
| | 72 |
| | 82 |
| | 94 |
| | 98 |

Grade 5: Form C

| | |
|--|----|
| Lightning crashes, thunder booms, and the earth shakes with the power of the storm. This storm is holding us captive in the lobby of the grocery store. Looking out the huge glass windows, we see an angry sky. It seems to be daring us to come outside and make a mad dash for our car. | 8 |
| | 20 |
| | 31 |
| | 43 |
| | 55 |
| Through the pelting rain we see our brave little minivan. It is just waiting for us to fill its trunk with the week's food and its seats with our bodies. | 67 |
| | 81 |

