b. Question 6: Have a simple test of near visual-motor skills (i.e. a board with small cut-out shapes that the subjects need to put in the correct place) and measure the time it takes them to complete it.

c. Question 7: Have a portable 3 to 5 shelf storage shelf with 20 random items. Ask the patient to find one specific item. Repeat 3 times and record the time it takes the patient for each attempt.

d. Question 11: Show the patient a 15-20 second video (without the audio track) showing a conversation between 2 individuals. Following the video, subjects will be queried about the facial expressions of the actors during the conversation.

4) Having the patient fill out a questionnaire based on the tests administered. Subjects are not excluded based on gender, age, or race. In total, there is a plan to have 1 visit for this project. It should be noted the collection of above mentioned clinical data points will solely be used for the purpose of this research study.

Study Procedures:

It is expected that approximately 20 Aston clinic patients will be enrolled in this trial. No bias or negative consequence will occur to anyone that does not wish to consider this project. After obtaining informed consent, the following procedures will be performed as an aspect of this study:

- Document patient demographics including age, sex, race, and ethnicity
- Review and document of medical and ophthalmic history
- Review and document Ophthalmic diagnosis (Retinal Degeneration or Diabetic Retinopathy) and onset time (in years and months if possible)
- Review and document concomitant use of systemic and ophthalmic therapies including administration of all laser and anti-VEGF therapies
- ETDRS Best Corrected Distance Visual Acuity will be performed
- Best Corrected Near Visual Acuity will be performed using a near card reader
- Wearing refraction (Glasses) will be measured and documented in source forms

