Periodically, the IRB will examine research studies conducted at UTSW Medical Center at Dallas. This audit process confirms whether a research project is being performed in an ethical manner, the protection of an individual who has given consent, and the researcher or his designee is following the regulatory codes of the university and government agencies such as FDA. All effort will be made to ensure patient confidentiality but there are times where the IRB representative will need to review the patient record to ensure that all elements of the study are being properly documented as specified in the protocol.

Potential Benefits:

The subjects may not receive direct medical benefit from taking part in the study. The knowledge gained from the study is to help define systems requirements for a device to assist low-vision persons with increased functionality. A \$100 stipend will be provided to patients to help offset any inconvenience from the 2 hours study visits.

Statistical Analysis Plan

A pilot study for this trial (8-10 subjects) will test the feasibility of improving sight for low-vision individuals. Statistical analysis will be performed on results based on the tests described in the protocol. Paired T-test analysis will be used to determine whether there are differences in vision and recognition when subjects are wearing or not wearing the sight enhancement device. Once the pilot study data shows that there may be differences vision using in relation to the testing parameters when

using the visual enhancement device, we will expand the study to a sample size of 20 individuals to collect data that will be sufficient to achieve appropriate statistical power and determine whether there is statistical significance between using vision using the enhanced vision device and vision without the device.

National Eye Institute
Visual Functioning Questionnaire - 25
(VFQ-25)

Version 2000

(INTERVIEWER ADMINISTERED FORMAT)

January 2000

RAND hereby grants permission to use the "National Eye Institute Visual Functioning Questionnaire 25 (VFQ-25) July 1996, in accordance with the following conditions which shall be assumed by all to have been agreed to as a consequence of accepting and using this document:

1. 1. Changes to the NEI VFQ-25 - July 1996 may be made without the written permission of RAND. However, all such changes shall be clearly identified as having been made by the recipient.

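### Test order (with or without the device) and the assignment of materials are neither set, balanced nor recorded, so order can be confounded with the device effect

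*Combined protocol and SAP*

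**What the plan says.** Study Procedures states that the functional tests "will be administered to each subject as outlined in previous section with and without the head mounted visual assessment device". The one provision that separates the two conditions is the rest period: "Patients will be given a 20-minute break between testing with and without the head mounted visual assessment device".

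The tests are described in Concise Summary of Project, item 3:

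- **Reading:** "Question 5: Reading speed using a standard paragraph". Three English and three Spanish texts are printed. None is tied to a condition.
- **Near visual-motor task, timed:** "a board with small cut-out shapes that the subjects need to put in the correct place". No second board is described.
- **Shelf search, three timed attempts:** "Have a portable 3 to 5 shelf storage shelf with 20 random items". Nothing is said about changing the targets or layout between conditions.
- **Facial expressions:** one short silent video followed by questions. No second clip is described.

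Sources of Research Material lists what source documents must support, including efficacy results and product administration. Test order and form are not on that list.

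The Statistical Analysis Plan says: "Paired T-test analysis will be used to determine whether there are differences in vision and recognition when subjects are wearing or not wearing" the device. It names no order, period or form term. The same comparison in the 8-10 subject pilot leads to expansion to 20: "Once the pilot study data shows that there may be differences vision using in relation to the testing parameters when" the device is used.

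**The concern.** The with/without comparison within subjects is the study's only efficacy contrast, and according to Concise Summary of Project "the primary objective of this testing is to establish the benefits of a wide field-of-view" head-mounted display. Each task can plausibly change on repetition within one visit of about 2 hours. A board already solved, a shelf already searched or a clip already seen may be easier the second time; tiredness would act the other way. Potential Risks also mentions possible disorientation, dizziness or blur, which could persist into a no-device session that follows device use. A 20-minute break may ease fatigue but does not erase memory.

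If order favours the device condition, a false benefit becomes more likely. If it opposes it, a real benefit is attenuated. If all subjects share one order, which the plan permits, order and device are fully confounded and no later analysis can separate them. The pilot that informs expansion is exposed in the same way.

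**Working it through.** **The plan's own figure.** The sample size of 20 cannot be reproduced, because no alpha, sidedness, power, effect size or SD is given. What follows is illustration under stated assumptions.

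**Inputs.** From the Statistical Analysis Plan: n = 20 and a paired t-test. Assumed: one endpoint, two-sided alpha 0.05, and normal differences d (device minus no device, signed so that positive favours the device) with SD 1 within each order. The second session is better by δ = 0.2, 0.3 or 0.5 SD. If the second session is worse (fatigue), exchange the two orders. The decision to expand after the pilot is not modelled, because the plan gives no criterion.

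**Model.** With true effect μ, the mean of d is μ + δ for subjects tested device-second and μ − δ for those tested device-first. With p the share tested device-second, the paired mean has expectation μ + (2p − 1)δ. The sum of squares is noncentral chi-square with 19 df and noncentrality 20δ²[1 − (2p − 1)²]. The chance that t exceeds its upper 2.5% point is obtained by numerical integration.

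**False benefit (μ = 0, nominal 2.5%), planned test:**

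| Device-second / device-first | δ = 0.2 | δ = 0.3 | δ = 0.5 |
|---|---|---|---|
| 10/10 | 2.3% | 2.1% | 1.5% |
| 12/8 | 3.4% | 3.7% | 4.0% |
| 14/6 | 4.9% | 6.4% | 9.6% |
| 16/4 | 7.0% | 10.6% | 20.1% |
| 20/0 | 13% | 25% | 56% |

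**Power when order opposes the device.** The effect with 80% power at n = 20 is 0.660 SD (noncentral t, 19 df).

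| Device-first / device-second | δ = 0.2 | δ = 0.3 | δ = 0.5 |
|---|---|---|---|
| 10/10 | 79% | 77% | 72% |
| 12/8 | 74% | 69% | 57% |
| 14/6 | 68% | 60% | 42% |
| 16/4 | 62% | 51% | 28% |
| 20/0 | 50% | 33% | 10% |

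A 10/10 split with the planned test is therefore valid but conservative: the shift cancels from the mean but inflates the variance.

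**With an order term.** The estimate is the average of the two order-group means. With group sizes a and b its variance is (1/a + 1/b)/4, so the effective sample size is 4ab/20 and there are 18 df.

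- 10/10: effective n 20; false benefit 2.5%, power 79.8%.
- 12/8: effective n 4·12·8/20 = 19.2; power 78%.
- 14/6: effective n 16.8; power 73%.
- 16/4: effective n 12.8; power 61%.

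False benefit returns to 2.5% in the unbalanced cases too, but only if order was recorded. At 20/0 the order term cannot be estimated.

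**Limit of balancing.** If device-first subjects then do worse without the device by c = 0.2, 0.4 or 0.6 SD (assumed), d rises by c in that half. The order-adjusted estimate keeps a bias of c/2, with noncentrality (c/2)√20, and false benefit is 6%, 13% or 25%.

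**Materials.** The printed English texts count to 98 (Form A), 93 (Form C) and 97 (Form D) words, and the Spanish texts are labelled 101, 101 and 102. Two conditions at one visit need two texts, and three exist. If the optional identical second visit is held, fresh text at each reading needs 2 × 2 = 4, one more than is printed.

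**The case against.** The strongest reply is that silence on order allows confounding but does not show it. The large figures need every subject to share one order, and even 14/6 or 16/4 needs a skew that no passage describes. If each subject's order were in effect a coin toss, averaging the model over all splits gives 2.5% false benefit at all three shifts. The power losses are also shown only at 0.66 SD: with all subjects device-first, a true effect of 1.0 SD still has 92%, 84% or 56% power, and 1.5 SD has at least 98.9%. Source forms and a CRF that are not part of the document might capture order, as might the video of the device session. Three paragraphs per language already allow different texts, and the second visit is only optional.

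All of this is fair about size, and the figures should be read as conditional. It does not remove the omission. No passage makes order haphazard rather than uniform, a fixed routine is as compatible with the text as a coin toss, and recovering order afterwards does not help if it was the same for all.

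A second reply concerns cost in the pilot, and it stands in part. Take the effect with 80% power at each pilot size and count lost df alone. Fitting order plus language-specific form terms then gives about 69% (two paragraphs per language) or 44% (three) at n = 8, and about 75% or 66% at n = 10. The order term alone gives about 78% and 79%. Form terms should therefore not be required at pilot size.

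**Conclusion.** The concern holds. The plan does not set or balance order, does not require order or form to be recorded, does not assign materials to conditions, and analyses the differences without an order term. As written it permits partial or complete confounding of order with the device, in a direction the document does not determine.

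The consequence ranges from almost none (a split near 10/10) to a false-benefit rate of 13% to 56%, or power of 50% to 10%, if all subjects share one order. Those ranges rest on assumed order shifts of 0.2 to 0.5 SD and an assumed two-sided alpha of 0.05. Confidence is high that the omission exists; its actual effect is unknown. This is a cheap improvement, and it has to be made before testing because a common order cannot be undone in analysis.

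**What to change.** - **Order.** Randomise 1:1 from a prepared list for each language, in blocks of four (two orders by two form assignments), each block built from two pairs that hold both orders. Order then stays within one subject of balance per language at any pilot size. Amend the non-randomised description of the study to say that test order is randomised.
- **Materials.** Use different paragraphs in the two conditions, rotate them within each order, and report words per minute because lengths differ. Change shelf targets and layout and, where available, the board and video.
- **Recording.** Add order and form as two fields for each subject.
- **Analysis.** Analyse the within-subject difference with an order (period) term and show results by order, because balancing does not remove differential carry-over. Leave form terms out at pilot size and rely on rotation.
- **Second visit.** If it is held, repeat the balancing with fresh materials, including at least one more paragraph per language.

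**Cost.** A short amendment, the lists, two recorded fields and alternate materials of comparable difficulty; no extra patients or visits. At n = 20 and 0.66 SD, the order term takes power from 80.0% to 79.8% (19 to 18 df). Form terms, if fitted, take it to 79.5%, 79.2% or 78.4% (17, 16 or 14 df), counting lost df alone. Unequal forms may add variance: an assumed extra SD of 0.25 or 0.5 lowers power to 77% or 70.5%, so comparability of the materials matters more than the df.
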